6.2 Inclusion Criteria

All patients must meet all of the following inclusion criteria:

1. Histologically or cytologically confirmed metastatic breast cancer relapsed or refractory to approved standard available treatment
 - Specifically, patients with HER2-positive disease, as defined by the American Society of Clinical Oncology/College of American Pathologists (ASCO/CAP) guidelines [51], must have exhausted approved HER2-directed therapies prior to enrollment
2. Prior treatment with standard first line therapy in the metastatic setting
3. *FGFR1* amplification or 11q amplification status determined on the most recent tumor tissue available, or detected in blood using validated methods for detecting circulating tumor cells (CTCs) or ctDNA:
 - a) Patients in Cohort A: *FGFR1*- or 11q-amplified
 - b) Patients in Cohort C: neither *FGFR1*- nor 11q-amplified

Patient amplification status will be based on:

- local assessment by FISH, NGS, CGH, CISH, or qPCR; or
 - local assessment in blood using validated methods for detecting circulating tumor cells (CTCs) or ctDNA; or
 - central assessment by FISH, as confirmed by a prescreening process
4. Availability of formalin-fixed paraffin embedded (FFPE) tumor tissue sufficient for the central confirmation by FISH of *FGFR1* amplification or 11q amplification status. Detailed sample handling instructions are provided in the Laboratory Manual
 5. Demonstrated progression of disease by radiological or clinical assessment
 - Measurable disease according to RECIST Version 1.1 is NOT required for enrollment
 6. Patient, aged ≥ 18 years old
 7. Eastern Cooperative Oncology group (ECOG) Performance status 0 or 1
 8. Estimated life expectancy > 6 months
 9. Normal left ventricular function defined as a left ventricular ejection fraction (LVEF) $\geq 50\%$ by ECHO or MUGA
 10. Screening for laboratory values within the following parameters:
 - Hematology: absolute neutrophil count (ANC) $\geq 1000/\text{mm}^3$; platelet count $\geq 100,000/\text{mm}^3$; hemoglobin ≥ 9 g/dL
 - Renal function:
 - Serum creatinine < 1.5 mg/dL or creatinine clearance > 45 mL/min (Modification of Diet in Renal Disease formula [MDRD])
 - Dipstick protein measurement $< 2+$. If dipstick $\geq 2+$ then perform 24-hour urine protein measurements and if proteinuria < 300 mg patient is eligible for inclusion
 - Liver function tests: total bilirubin ≤ 1.5 upper limit of normal (ULN; unless evidence of Gilbert's disease confirmed by uridine diphosphate-glucuronyltransferase [UGT] polymorphism); aspartate transaminase (AST) and alanine transaminase (ALT) ≤ 3 ULN; AST and ALT ≤ 5 ULN in case of liver metastases
 11. For women with childbearing potential, a negative pregnancy test within 7 days prior to initiation of the study drug
 12. Willingness to use an effective contraceptive method during the study and up to six months after the last dose is administered. Effective methods include the following: non-hormonal intrauterine device, barrier method (condoms, diaphragm) also in conjugation with spermicidal jelly, or total abstinence. Oral, injectable, or implant hormonal contraceptives are discouraged
 13. Written consent on an Institutional Review Board (IRB)/Independent Ethics Committee(IEC)-approved ICF prior to any study-specific evaluation

6.3 Exclusion Criteria

Any of the following criteria will exclude patients from study participation:

1. Current or recent treatment with biologic anticancer therapies. Required washout for prior biologic anticancer therapies:
 - 3 months for bevacizumab
 - 28 days or five half-lives, whichever is shorter, for all other biologic therapies
2. Ongoing AEs from prior anticancer therapies, including radiation, targeted or cytotoxic therapies without resolution of any Grade 2 or greater side effects to Grade ≤ 1
3. Current treatment with any prohibited medications associated with prolongation of QT interval and known risk of Torsades de Pointes (see [Appendix C](#))
4. Active CNS metastases, as indicated by clinical symptoms, cerebral edema, and/or progressive growth (patients with history of CNS metastases or cord compression are eligible if they are clinically stable for at least 4 weeks before first dose of lucitanib and do not require high-dose steroid treatment)
5. History of clinically significant or uncontrolled cardiac disease, including congestive heart failure (HF; New York Heart Association functional classification ≥ 3), angina, myocardial infarction within 6 months, or ventricular arrhythmia
6. QT_C prolongation (defined as a QT_C interval >470 msec according to Fridericia's correction)
7. Uncontrolled hypertension (defined as systolic blood pressure [SBP] ≥ 140 mmHg and/or diastolic blood pressure [DBP] ≥ 90 mmHg with optimized anti-hypertensive therapy)
 - The requirement for >2 anti-hypertensives to control hypertension at time of enrollment is exclusionary
8. Active second malignancy, i.e., patient known to have potentially fatal cancer present for which he/she may be (but is not necessarily) currently receiving treatment
 - Patients with a history of malignancy that has been completely treated, with no evidence of that cancer currently, are permitted to enroll in the trial provided all chemotherapy was completed >6 months prior and/or bone marrow transplant (BMT) >2 years prior
9. Uncontrolled hypothyroidism defined as serum thyroid stimulating hormone (TSH) higher than 5 mIU/mL while receiving optimized thyroid hormone replacement therapy
10. Patient with history of thrombotic disorders:
 - Any history of venous thrombotic events, deep vein thrombosis (with the exception of catheter related deep vein thrombosis), or pulmonary embolism within 6 months prior to the first dose of lucitanib
 - Any history of arterial thrombotic events, cerebrovascular accident, or transient ischemic accident within 6 months prior to the first dose of lucitanib

- Any peripheral vascular disease or vasculitis which required treatment within 6 months prior the first dose of lucitanib
 - Patient with hereditary risk factors of thromboembolic events (e.g., mutation of the Factor V of Leiden)
11. Received administration of strong inhibitors of CYP2C8 or CYP3A4 or strong inducers of CYP3A4 ≤ 7 days prior to first dose of lucitanib or have on-going requirements for these medications ([Appendix E](#))
 12. Received investigational treatment within 28 days prior to enrollment in this study
 13. Non-study related minor surgical procedures ≤ 14 days prior to administration of lucitanib. In all cases, the patient must be sufficiently recovered and stable before treatment administration
 14. History of major surgical procedure or significant trauma within 28 days prior to lucitanib. In all cases, the patient must be sufficiently recovered and stable before treatment administration
 15. Females who are pregnant or breastfeeding
 16. Presence of any serious or unstable concomitant systemic disorder incompatible with the clinical study (e.g., substance abuse, uncontrolled psychiatric condition, uncontrolled intercurrent illness including active infection, arterial thrombosis, and symptomatic pulmonary embolism)
 17. Foreseeable poor compliance to the study procedures
 18. Any other reason the investigator considers the patient should not participate in the study

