---	--

Study Population (continued)
	
13. Written consent on an Institutional Review Board (IRB)/Independent Ethics Committee (IEC)-approved Informed Consent Form (ICF) prior to any protocol-specific evaluation
 
Exclusion Criteria
 
Any of the following criteria will exclude patients from study participation:
 
 1. Current or recent treatment with biologic anticancer therapies. Required washout for prior biologic anticancer therapies: 
 ◦ 3 months for bevacizumab ◦ 28 days or five half-lives, whichever is shorter, for all other biologic therapies 2. Ongoing AEs from prior anticancer therapies, including radiation, targeted or cytotoxic therapies without resolution of any Grade 2 or greater side effects to Grade ≤ 1 3. Current treatment with any prohibited medications associated with prolongation of QT interval and known risk of Torsades de Pointes (see Appendix C) 4. Active central nervous system (CNS) metastases, as indicated by clinical symptoms, cerebral edema, and/or progressive growth (patients with history of CNS metastases or cord compression are eligible if they are clinically stable for at least 4 weeks before first dose of lucitanib and do not require high-dose steroid treatment) 5. History of clinically significant or uncontrolled cardiac disease, including congestive heart failure (HF; New York Heart Association functional classification ≥ 3), angina, myocardial infarction within 6 months, or ventricular arrhythmia 6. QT_C prolongation (defined as a QT_C interval >470 msec according to Fridericia's correction) 7. Uncontrolled hypertension (defined as systolic blood pressure [SBP] ≥ 140 mmHg and/or diastolic blood pressure [DBP] ≥ 90 mmHg with optimized anti-hypertensive therapy) 
 ◦ The requirement for >2 anti-hypertensives to control hypertension at time of enrollment is exclusionary 8. Active second malignancy, i.e., patient known to have potentially fatal cancer present for which he/she may be (but is not necessarily) currently receiving treatment 
 ◦ Patients with a history of malignancy that has been completely treated, with no evidence of that cancer currently, are permitted to enroll in the trial provided all chemotherapy was completed >6 months prior and/or bone marrow transplant (BMT) >2 years prior 9. Uncontrolled hypothyroidism defined as serum thyroid stimulating hormone (TSH) higher than 5 mIU/mL while receiving optimized thyroid hormone replacement therapy 10. Patient with history of thrombotic disorders: 
 ◦ Any history of venous thrombotic events, deep vein thrombosis (with the exception of catheter related deep vein thrombosis), or pulmonary embolism within 6 months prior to the first dose of lucitanib ◦ Any history of arterial thrombotic events, cerebrovascular

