6.5 Waivers of Inclusion/Exclusion Criteria

No waivers of these inclusion or exclusion criteria will be granted by the investigator and the sponsor or its designee for any patient enrolling into the study.

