7.4.2 Proteinuria

Patients will be monitored for proteinuria by dipstick every two weeks during Cycle 1 and Cycle 2 and every 28 days thereafter. Patients with early signs of proteinuria by dipstick (2+) should be closely monitored and proteinuria evaluated quantitatively (24 hours protein excretion or protein-to-creatinine ratio). Additional safety monitoring should be performed as clinically indicated including tests for the assessment of free/conjugated bilirubin, haptoglobin N, schizocytes, or renal biopsy.

The following treatment and lucitanib dose adjustments algorithm should be followed in case proteinuria is encountered:

Table 3: Proteinuria Management Algorithm

In case of first onset of proteinuria \geq Grade 2 (i.e., ≥ 1 g in 24 hours by quantitative assessments)	Lucitanib treatment should be withheld and proteinuria monitored by dipstick twice weekly. Upon recovery of proteinuria to Grade ≤ 1 (1+ by dipstick or urinary protein < 1.0 g/24 hours), lucitanib treatment should be resumed at the same dose and dipstick monitoring should continue
In case of second onset of proteinuria \geq Grade 2	Withhold the drug and perform a quantitative assessment of 24-hour urinary protein. Upon recovery, the lucitanib treatment should be resumed with a 2.5 mg dose reduction (e.g., 10 mg to 7.5 mg)
In case of third onset of proteinuria \geq Grade 2	Repeat assessments and dose modifications as outlined above (e.g., 7.5 mg to 5 mg)
In case of fourth onset of proteinuria \geq Grade 2	If proteinuria \geq Grade 2 recurs following dose reductions to 5 mg, or if there is no recovery within 30 days, discontinue treatment permanently

In case of Grade 3 proteinuria or of additional risk factors (e.g., microhematuria, arterial hypertension), assessment of free/conjugated bilirubin, haptoglobin N, schistocytes, and/or renal biopsy may be indicated in consultation with a nephrologist.

Proteinuria will be graded as follows (CTCAE Version 4.0):

Grade 1: 1+ proteinuria; urinary protein < 1.0 g/24 hours

Grade 2: 2+ proteinuria; urinary protein ≥ 1.0 –3.4 g/24 hours

Grade 3: Urinary protein ≥ 3.5 g/24 hours

7.4.3 *Sub-clinical hypothyroidism*

Plasma TSH and thyroid hormones levels should be measured, per protocol. Treatment with levothyroxine 50 µg/day is recommended for patients with TSH values above 5 mIU/L, even if triiodothyronine (T3) and thyroxine (T4) are normal. The treatment with lucitanib can continue at the same dose.

7.4.4 *Decrease in LVEF*

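### The TSH limit in exclusion criterion 9 is written per mL and the on-study TSH action level per L, so the same number 5 stands for values 1000-fold apart and the passages must be reconciled

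*Protocol*

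**What the plan says.** **Eligibility.** Protocol Section 6.3, exclusion criterion 9, reads "Uncontrolled hypothyroidism defined as serum thyroid stimulating hormone (TSH) higher than 5 mIU/mL while receiving optimized thyroid hormone replacement therapy". Criterion 9 in the synopsis has the same limit in the same unit: "higher than 5 mIU/mL while receiving optimized thyroid hormone replacement therapy".

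**On-study management.** Section 7.4.3 (Sub-clinical hypothyroidism) says that levothyroxine "is recommended for patients with TSH values above 5 mIU/L, even if triiodothyronine (T3) and thyroxine (T4) are normal", and that lucitanib can continue at the same dose. The synopsis gives the same level in the same unit.

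**Related text.**
- The screening laboratory limits in inclusion criterion 10 cover hematology, renal function and liver tests, but not thyroid function.
- TSH is part of the serum chemistry panel, which local laboratories run at screening and on Cycle 1 Day 1 (Tables 4 and 5).
- Section 6.5 states: "No waivers of these inclusion or exclusion criteria will be granted by the investigator and the sponsor or its designee".
- SAP Section 7 plans a listing of the number of patients who violate each criterion. The SAP gives no TSH limit of its own.

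**The concern.** The analyte and the numeral are the same in all four places. The volume unit is per mL in the two eligibility statements and per L in the two management statements, and no passage gives a reason.

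Criterion 9 is the only numeric thyroid limit at entry, so its unit decides whom it excludes. Hypothyroidism is among the most frequently reported treatment-emergent events (Section 3.6.1.3), so thyroid status at entry bears on how on-study thyroid findings are read. About 30–40 sites are planned, each using local laboratories. The protocol does not tell a site whether to apply the limit as printed or to read it in the unit of Section 7.4.3. The same uncertainty reaches whoever prepares the violation listing, because the set of patients counted against criterion 9 depends on the unit used.

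**Working it through.** The plan derives no figure here, so there is nothing to reproduce. The check is a unit conversion followed by a comparison of passages.

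**Inputs**

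| Item | Where | As written |
|---|---|---|
| Exclusion limit | Protocol 6.3 and synopsis, criterion 9 | TSH > 5 mIU/mL |
| On-study action level | Protocol 7.4.3 and synopsis | TSH > 5 mIU/L |

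**Conversion.** 1 L = 1000 mL, so 1 mIU/mL = 1000 mIU/L.

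- Exclusion limit: 5 × 1000 = 5000 mIU/L.
- Ratio to the action level: 5000 / 5 = 1000.
- In the other direction: 5 mIU/L = 5 / 1000 = 0.005 mIU/mL.

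**Criterion 9 read literally**, for a patient on optimized replacement:

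| TSH (mIU/L) | TSH (mIU/mL) | Multiple of the 5 mIU/L action level | Meets criterion 9 as written? |
|---|---|---|---|
| 6 | 0.006 | 6 / 5 = 1.2 | No |
| 40 | 0.04 | 40 / 5 = 8 | No |
| 500 | 0.5 | 500 / 5 = 100 | No |

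These TSH values are illustrations, not expected results. The documents give no TSH distribution.

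**Could another criterion catch such a patient?** None does so by a thyroid number. Criterion 16 (serious or unstable systemic disorder) and criterion 18 (any other reason in the investigator's view) could, by judgment. Criterion 2 could if the abnormality were an unresolved Grade 2 or greater effect of earlier anticancer therapy.

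**Is it a PDF reading error?** This is unlikely. The per-mL unit appears in two separate places. Micro signs survive elsewhere in the same text: in the levothyroxine dose in Section 7.4.3 and the synopsis, and in the hERG concentration in Section 3.5.1.2.

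**The case against.** The strongest reply is that the two limits do different jobs. Criterion 9 concerns patients already on optimized replacement. Section 7.4.3 recommends starting levothyroxine on study, even with normal T3 and T4, and lets lucitanib continue. They need not be equal, and that stands. But a difference in purpose does not explain an identical numeral with units 1000-fold apart.

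A second reply is that many sites would take the unit for a slip and apply the limit sensibly. That may be so, but the documents do not say it.

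Several stronger readings are tempting, and the documents do not support them:

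- **That criterion 9 excludes nobody.** No TSH reference range or distribution is given. What is shown is a limit 1000 times the action level.
- **That every patient between 5 and 5000 mIU/L is admitted.** Not meeting one exclusion is not admission. Criteria 2, 16 and 18 remain, and the investigator must review the chemistry panel before dosing starts (Table 4 and Table 5 footnotes).
- **That Section 6.5 binds sites to enroll such patients.** It bars waivers of the criteria. It does not oblige a site to enroll anyone.
- **That lucitanib is known to worsen existing hypothyroidism.** Section 3.6.1.3 lists hypothyroidism as a frequent treatment-emergent event and says that most of the common events other than hypertension were Grade 1 or 2. It says nothing about pre-existing disease.
- **That the SAP listing would flag no violation.** SAP Section 7 does not say how violations are identified.

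A micro sign misread in both places cannot be ruled out entirely from the extracted text, since 5 microIU/mL equals 5 mIU/L. The surviving micro signs make it improbable.

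**Conclusion.** The inconsistency is real, and its size is exact: a factor of 1000 between the exclusion limit and the action level for the same analyte. Applied as printed, criterion 9 does not exclude patients on optimized replacement whose TSH is well above the level at which the protocol itself recommends treatment, and exclusion then rests on judgment-based criteria.

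The conclusion assumes only that the extracted units match the source document. It does not say which limit is clinically right, and it makes no estimate of how many patients are affected. Criterion 9 reaches only patients already on replacement, so the group concerned is narrower than all patients with raised TSH.

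The issue is confined to eligibility and the violation listing. Sample size, the PFS definition and the primary analysis do not depend on it. It should be corrected because it is an operative threshold, but it does not threaten the main results.

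**What to change.** - The sponsor confirms the intended exclusion limit.
- Criterion 9 in Section 6.3 and in the synopsis then states that limit in the unit of Section 7.4.3 and its synopsis counterpart, so that one local laboratory result can be compared with both levels directly.
- Any eligibility check, and the SAP Section 7 listing, use that unit. Because patients were already on study (Section 3.6.1.3 counts 43 at the May 2015 data cutoff), the listing should state which limit it applies.

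The cost is a text correction in two places and one clarifying line in the SAP. No new test is needed, because TSH is already in the screening panel.

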6.4 Patients or Partners of Patients of Reproductive Potential

Pregnancy is an exclusion criterion and women of childbearing potential must not be considering getting pregnant, or become pregnant, during the study. Female patients who are more than 2 years postmenopausal or have had a hysterectomy will not be considered of childbearing potential. Female patients of childbearing potential must have a negative serum pregnancy less than 7 days prior to administration of the first dose lucitanib. If the serum pregnancy results are not available prior to dosing, a urine pregnancy test can be performed to confirm that the patient is not pregnant prior to dosing. Both values should be entered in the electronic case report form (eCRF). Another serum pregnancy test will be performed at the end-of-study visit.

Patients of reproductive potential (males and females) must practice an effective method of contraception during treatment and for 6 months following the last dose of lucitanib. Adequate contraception is defined as double-barrier method (i.e., condom plus spermicide in combination with a diaphragm, cervical/vault cap, or intrauterine device). Oral, injectable, or implant hormonal contraceptives are discouraged.

Patients will be instructed to notify the investigator if pregnancy is discovered either during or within 6 months of completing treatment with lucitanib. This also applies to male patients whose

partners become pregnant while the patient is on study, or within the 6-month period after the last dose of lucitanib.

6.5 Waivers of Inclusion/Exclusion Criteria

No waivers of these inclusion or exclusion criteria will be granted by the investigator and the sponsor or its designee for any patient enrolling into the study.

7 DESCRIPTION OF STUDY TREATMENTS AND DOSE MODIFICATIONS

7.1 Description of Study Treatments

Lucitanib is supplied as an oral formulation as either hard gelatin capsules or tablets. A brief description of the investigational product is provided below (additional information may be found in the Investigator’s Brochure and pharmacy manual):

Drug name:	CO-3810	
International Nonproprietary Name (INN):	lucitanib	
	Capsules	Tablets
Formulation:	2.5 mg (orange and white size 4), 5 mg (orange size 4), and 10 mg (white size 4)	5 mg (white), 7.5 mg (pink)
Excipients:	lactose monohydrate, sodium croscarmellose, and magnesium stearate	glycerol, pregelatinized starch, hydroxypropylmethyl cellulose, and magnesium stearate, polyethylene glycol 6000, titanium dioxide, iron oxide (7.5 mg only)
Temperature storage conditions:	59 – 77°F / 15 – 25°C	59 – 86°F / 15 – 30°C

Lucitanib is packaged in child-resistant tamper evident high-density polyethylene (HDPE) bottles. Bottles with capsules will contain desiccant. Lucitanib will be supplied to the study sites by the sponsor. Lucitanib supplies should be stored in their original packaging and not refrigerated. Each bottle of study drug will contain the unique identification code and the LOT number.

At the start of each cycle, the patient will receive sufficient lucitanib supplies to complete 4 weeks of treatment.

Bottles containing lucitanib will be labeled according to national regulations for investigational products. The expiry date will not appear on the labels, but will be controlled by the use of an Interactive Web Response System (IWRS).

7.2 Method of Assigning Patients to Treatment Groups

After confirming that patients fulfill entry criteria, the Investigator or his/her delegate will enroll patients as follows:

- Cohorts A and C (non-PK sub study patients): enrollment in IWRS on C1D1 to receive lucitanib at 10 mg daily*
- PK sub study patients: manual enrollment at Day -7 visit to receive single dose of 10 mg lucitanib in a tablet formulation, followed by enrollment in IWRS on C1D1 to receive lucitanib at 10 mg daily*

Based on analysis of data from the PK sub study and confirmation of acceptable PK comparability, patients may begin lucitanib treatment with the tablet formulation upon enrollment and patients who began treatment with capsule formulation may, at the discretion of the Sponsor and Investigator, be switched to the tablet formulation.

*Treatment should be initiated within 3 days of enrollment.

